## 7.9.1 Primary Endpoint

The primary endpoint is the Change from Baseline in Abdominal Score at Each Week during the Treatment Period. The weekly Abdominal Score is the average of the non-missing daily Abdominal Scores during in a week. Change from baseline will be calculated as the weekly score minus the baseline score.

### 7.9.1.1 *Analyses of the Primary Endpoint*

Inferential testing between the linaclotide 290 µg and placebo groups with regard to the change from baseline in abdominal score over the Treatment Period will be evaluated employing a mixed model with repeated measures (MMRM) framework with week (categorical), treatment, geographic region, and week-by-treatment fixed effects, patient as the random effect, and baseline value as a covariate. An unstructured covariance structure will be utilized to model the covariance matrix. Descriptive statistics based on the MMRM model will include least-squares (LS) mean change from baseline for each treatment, the LS mean difference between linaclotide 290 µg and placebo, corresponding 95% CIs, and the p-value associated with the comparison.

### 7.9.1.2 *Sensitivity Analyses of the Key Efficacy Parameters*

If warranted, for the primary efficacy and secondary endpoints/analyses (defined in Section 7.9.2), the potential impact of missing data on the estimates of treatment effect will be assessed using a sensitivity analysis approach based on multiple imputations (MI).

In order to characterize the extent of missing data associated with the key efficacy parameter, the number and percentage of patients with <4 completed evening diaries will be presented by treatment group for the ITT Population for each week of the Treatment Period (Please refer to Section 7.8 for additional details).

Weekly data for a patient with <4 complete evening diaries in a week will be classified as missing for that week. Sensitivity analyses will utilize a pattern-mixture model using a placebo-based method (3).

The placebo-based MI imputes missing data after dropout (monotonic) based on the placebo group data using multiple imputation methodology for all subjects (including active treatment subjects).

The steps to implement placebo-based MI are as follows:

1. **Create a Monotonic Dataset:** One-thousand (1000) datasets will be generated where missing outcome data at intermittent week (s) (non-monotonic) will be first imputed for each treatment using non-missing data from all subjects within the treatment group by a Monte Carlo Markov Chain (MCMC) imputation model with treatment, baseline score, geographic region and weekly score. The MCMC statement (mcmc chain=multiple impute=monotone) in the SAS PROC MI procedure will be used. As a result, each of the 1000 datasets will only have missing ending data, or a monotone missing data pattern.
2. For each of the 1000 datasets with monotonic missing data, the monotonic missing weekly data will be imputed one week at a time by a sequence of MIs, as follows. Imputation will utilize data from all Placebo subjects and Active treatment with the week of interest (week currently being imputed) missing.
  - a. For week 1, create two datasets: one containing all placebo patients and active patients with the week 1 value - missing, referred to as Mono\_imp1; one containing all other patients, referred to as Mono\_rest1.
  - b. For Mono\_imp1, impute the missing values at week 1 utilizing Proc MI:

```
PROC MI data=mono_imp1 out=reg_imp1 n impute=1 seed=XXXX;  
  By imputation; /*note 1000 imputation performed in step 1*/  
  Var base siteid change1;  
  Monotone Regression (change1);  
 Run;
```

- c. Set Mono\_rest1 and reg\_imp1 Call this dataset IMP1.
- d. Repeat Steps 2a-2c for weeks 2 through 12, respectively

Note: for Week i, i>1,

```
PROC MI data=mono_impi out=reg_impi n impute=1 seed=XXXX;  
  By imputation; /*note 1000 imputation performed in step 1*/  
  Var base siteid change1 change2 . . . change(i-1) change(i);  
  Monotone regression (change(i));  
 Run;
```

3. Analyze each of the 1000 imputed complete datasets.
  - a. For continuous endpoints, perform same statistical analyses (MMRM) as described in Section 7.9.1.1 for observed case.
  - b. For responder endpoint:
    - a. Using the abdominal score data imputed above, recalculate the responder

- b. For each imputed dataset, perform Cochran-Mantel-Haenszel (CMH) analyses as described in Section 7.9.2.1.
4. Estimation and Inference of the MI datasets will be performed using Rubin's combination rules (4) as implemented through the MIANALYZE procedure in SAS.

## 7.9.2 Secondary Efficacy Endpoints

The secondary efficacy endpoints are:

- Change from Baseline in 12-week Abdominal Score  
The 12-week Abdominal Score is the average of the non-missing Abdominal Scores reported over the course of the Treatment Period. Change from baseline will be calculated as the 12-week score minus the baseline score.
- 6/12 Week Abdominal Score Responder  
A 6/12 Week Abdominal Score Responder is a patient who meets the Weekly Abdominal Score Responder criteria for at least 6 out of the 12 weeks of the Treatment Period. For each week in the Treatment Period, a Weekly Abdominal Score Responder is a patient who has an improvement from baseline of at least 2 points (ie, a -2 change from baseline) in the respective weekly abdominal score.

### 7.9.2.1 Secondary Efficacy Analysis

The cumulative distribution functions (CDFs) for linaclotide 290 µg and placebo will be estimated for the Change from Baseline in 12-week Abdominal Score endpoint. The CDFs will be compared using the Wilcoxon rank sum test with Hodges-Lehmann estimator for the median difference.

For the secondary responder endpoint, the proportion of responders in the linaclotide 290 µg group will be compared to the proportion of responders in the placebo group using a Cochran-Mantel-Haenszel (CMH) test controlling for geographic region. The number and percent of responders, the difference in responder rates between the linaclotide 290 µg and placebo groups, the odds ratio relative to placebo controlling for geographic region, all corresponding 95% CIs, and the p-value associated with the CMH test will be presented. The 95% CIs for responder rates will be obtained using exact Clopper-Pearson method; 95% CIs for differences in responder rates will be obtained using the normal approximation to the binomial distribution.

A secondary time-course analysis of the Change from Baseline in Abdominal Score (see primary endpoint definition in Section 7.9.1.1) will also be conducted. Using the MMRM framework defined in the primary analyses, treatment difference between linaclotide 290 µg and placebo will be assessed at each individual week. For each week, descriptive statistics based on the MMRM model will include the LS mean change from baseline for each treatment, the LS mean difference between linaclotide 290 µg and placebo, corresponding 95% CIs, and the p-value associated with the treatment comparison. Only weeks 12, 10, 8, 6, 4, 2, and 1 are secondary analyses controlled for multiplicity.

### **7.9.3 Additional Efficacy Endpoints**

Additional efficacy endpoints will be explored outside of the formal testing procedures and not controlled for multiplicity. These endpoints will include:

- 6/12 Week Abdominal Pain and Constipation (APC) +1 Responder

A 6/12 Week APC +1 Responder is a patient who meets the Weekly APC +1 Responder criteria for at least 6 out of the 12 weeks of the Treatment Period. For each week in the Treatment Period, a Weekly APC +1 Responder is a patient who has an increase from baseline of at least 1 in the respective CSBM weekly rate and has a decrease from baseline of at least 30% in the respective weekly abdominal pain score. If a patient did not enter information into the eDiary on at least 4 days for a particular Treatment Period week, the patient will not be considered a responder for that week.

- Change from Baseline in Abdominal Pain at Each Week

Abdominal pain is measured daily using an 11-point NRS. For each week on treatment, the weekly abdominal pain score is the mean of the non-missing daily values.

- Change from Baseline in CSBM Frequency Rate at Each Week

A patient's weekly CSBM frequency rate is the CSBM rate (CSBMs/week) calculated for that week.

- Change from Baseline in SBM Frequency Rate at Each Week

A patient's weekly SBM frequency rate is the SBM rate (SBMs/week) calculated for that week.

- Change from Baseline in BSFS (Stool Consistency) at Each Week

Stool consistency is measured using the 7-point BSFS. The patient's BSFS score for each week on treatment is the mean of the non-missing BSFS scores from the SBMs reported by the patient during the week.

- Change from Baseline in Stool Consistency at Each Week

Stool consistency is measured using a 5-point ordinal scale. The patient's stool consistency score for each week on treatment is the mean of the non-missing stool consistency scores from the SBMs reported by the patient during the week.

- Change from Baseline in Straining at Each Week

Straining is measured using a 5-point ordinal scale. The patient's straining score for each week on treatment is the mean of the non-missing straining scores from the SBMs reported by the patient during the week.

- Change from Baseline in Abdominal Discomfort at Each Week

Abdominal discomfort is measured daily using an 11-point NRS. For each week on treatment, the weekly abdominal discomfort score is the mean of the non-missing daily values.

- Change from Baseline in Abdominal Bloating at Each Week

Abdominal bloating is measured daily using an 11-point NRS. For each week on treatment, the weekly abdominal bloating score is the mean of the non-missing daily values.

- Percent Change from Baseline in Abdominal Pain at Each Week

Percent change will be calculated as  $100 * \text{the Change from Baseline in Abdominal Pain at Worst at each week divided by the baseline abdominal pain score.}$

- Change from Baseline in Percent of Days with Use of Rescue Medicine over the Treatment Period

The percent of days using per-protocol rescue medicine or any other laxative, suppository, or enema during each week will be calculated as  $100 * \text{the number of days rescue medicine was used during the week divided by the total number of days on treatment.}$

- SBM Within 24 Hours After First Dose Responder

A patient meets the SBM Within 24 Hours After First Dose Responder criteria if the amount of time between the randomization date and time and the time of first reported SBM is less than or equal to 24 hours. For patients who did not take their first dose of study medication on the randomization visit, then the first reported SBM must occur on the same study day as the first dose study day. Randomization date and time is utilized as a surrogate for the date and time of first dose because only first dose date, not time, is captured.

- 6/12 Week Abdominal Pain 30% Responder

A 6/12 Week Abdominal Pain 30% Responder is a patient who meets the Weekly Abdominal Pain 30% Responder criteria for at least 6 out of the 12 weeks of the Treatment Period. For each week in the Treatment Period, a Weekly Abdominal Pain 30% Responder is a patient who has a decrease from baseline of at least 30% in the respective weekly abdominal pain score. If a patient did not enter information into the eDiary on at least 4 days for a particular Treatment Period week, the patient will not be considered a Weekly Abdominal Pain 30% Responder for that week.

- 6/12 Week Abdominal Pain Responder

A 6/12 Week Abdominal Pain Responder is a patient who meets the Weekly Abdominal Pain Responder criteria for at least 6 out of the 12 weeks of the Treatment Period. For each week in the Treatment Period, a Weekly Abdominal Pain Responder is a patient who has an improvement from baseline of at least 2 points (ie, a -2 change from baseline) in the respective weekly abdominal pain score. If a patient did not enter information into the eDiary on at least 4 days for a particular Treatment Period week, the patient will not be considered a Weekly Abdominal Pain Responder for that week.

- 6/12 Week Abdominal Discomfort Responder

A 6/12 Week Abdominal Discomfort Responder is a patient who meets the Weekly Abdominal Discomfort Responder criteria for at least 6 out of the 12 weeks of the Treatment Period. For each week in the Treatment Period, a Weekly Abdominal Discomfort Responder is a patient who has an improvement from baseline of at least 2 points (ie, a -2 change from baseline) in the respective weekly abdominal discomfort score. If a patient did not enter information into the eDiary on at least 4 days for a particular Treatment Period week, the patient will not be considered a Weekly Abdominal Discomfort Responder for that week.

- 6/12 Week Abdominal Bloating Responder

A 6/12 Week Abdominal Bloating Responder is a patient who meets the Weekly Abdominal Bloating Responder criteria for at least 6 out of the 12 weeks of the Treatment Period. For each week in the Treatment Period, a Weekly Abdominal Bloating Responder is a patient who has an improvement from baseline of at least 2 points (ie, a -2 change from baseline) in the respective weekly abdominal bloating score. If a patient did not enter information into the eDiary on at least 4 days for a particular Treatment Period week, the patient will not be considered a Weekly Abdominal Bloating Responder for that week.

- 6/12 Week CSBM Responder

A 6/12 Week CSBM Responder is a patient who meets the Weekly CSBM Responder criteria for at least 6 out of the 12 weeks of the Treatment Period. For each week in the Treatment Period, a Weekly CSBM Responder is a patient who has an increase from baseline of at least 1 in the respective CSBM weekly rate. If a patient did not enter information into the eDiary on at least 4 days for a particular Treatment Period week, the patient will not be considered a Weekly CSBM Responder for that week.

- Treatment Satisfaction

Treatment satisfaction is measured on a 5-point ordinal scale. Treatment satisfaction will be analyzed separately for each Treatment Period week.

- Adequate Relief

Assessment of adequate relief during the previous 7 days is measured on a binary scale (yes/no). Assessment of adequate relief will be analyzed separately for each Treatment Period week.

- 6/12 Week Adequate Relief Responder

A 6/12 Week Adequate Relief Responder is a patient who reports Adequate Relief for at least 6 out of the 12 weeks of the Treatment Period.

- Change from Baseline in Constipation Severity

Constipation severity is measured weekly using a 5-point ordinal scale. Change from baseline will be calculated at each week.

- Change from Baseline in IBS Symptom Severity

IBS symptom severity is measured weekly on a 5-point ordinal scale. Change from baseline will be calculated at each week.

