### **3.3 LINACLOTIDE CLINICAL DEVELOPMENT**

The clinical development program for LINZESS® that culminated in FDA approval for use in adult patients with IBS-C included two large double-blind, placebo-controlled registration trials.(12, 13) These trials evaluated the safety and efficacy of linaclotide at a dose of 290 µg, administered as an oral capsule. One trial had a 26-week Treatment Period and one trial had a 12-week Treatment Period followed by a 4-week Randomized Withdrawal Period; however, the overall design of both Phase 3 trials was identical through the first 12 weeks of the Treatment Period. Both trials met all pre-specified primary and secondary efficacy endpoints. For each of the four primary efficacy parameters, the linaclotide dose group in both trials had statistically significantly higher proportions of responders compared with placebo (controlling for multiplicity). For all secondary efficacy change-from-baseline parameters (including complete spontaneous bowel movement [CSBM] frequency rate, spontaneous bowel movement [SBM] frequency rate, stool consistency, straining, abdominal bloating, abdominal discomfort, abdominal pain, and abdominal pain-free days) and responder parameters (6/12 Week CSBM +1 Responder and 6/12 Week Abdominal Pain Responder), the linaclotide group demonstrated statistically significant improvement compared with the placebo group (p<0.01 for all secondary parameters controlling for multiplicity) in both trials.

Linaclotide was well-tolerated in these trials.(12, 13) There were no deaths. One patient died during the Screening Period but never received either linaclotide or placebo. There were a total of 15 SAEs in the 2 trials. There were 9 (1.1%) SAEs in placebo-treated patients and 6 (0.7%) SAEs in linaclotide-treated patients. Overall, there was no obvious pattern in the types of SAEs experienced in either the placebo or linaclotide group. There were no SAEs of diarrhea. Treatment-emergent AEs (TEAEs) occurred in 54.9% of placebo-treated and 60.8% of linaclotide-treated patients. Diarrhea was the most frequent TEAE and was reported in 3.0% of patients treated with placebo and 19.8% of patients treated with linaclotide. Diarrhea was generally mild to moderate in severity. Diarrhea resulted in the discontinuation of 0.4% of patients treated with placebo and 5.3% treated with linaclotide.

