#### **4. TRIAL OBJECTIVES**

The objective of this trial is to evaluate the efficacy on abdominal symptoms (abdominal bloating, abdominal discomfort, and abdominal pain) and safety of linaclotide 290 µg administered orally to patients with irritable bowel syndrome with constipation (IBS-C).

[figure not shown]

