#### **10.4.5 Controlling for Multiplicity**

The overall family-wise Type I error rate for the primary and secondary efficacy analyses will be controlled at the  $\alpha=0.05$  level by employing a fixed-sequence procedure as described below. Following the fixed-sequence procedure, if the primary hypothesis between the placebo group and the linaclotide 290  $\mu$ g group is statistically significant ( $\alpha=0.05$ ) in the ITT Population, then the primary objective of the trial will have been achieved and the next hypothesis can be tested; otherwise, testing will stop. The testing of each sequential hypothesis is conditional on all the previous hypotheses being rejected at the 0.05 level of significance. If a hypothesis is not rejected at the 0.05 level of significance, then all remaining hypotheses are deemed not statistically significant. All hypothesis testing will be two-sided.

1. Linaclotide vs. placebo – Change from Baseline in Abdominal Score (primary efficacy analysis)
2. Linaclotide vs. placebo – Change from Baseline in 12-week Abdominal Score (CDF) (secondary efficacy analysis)
3. Linaclotide vs. placebo – 6/12 Week Abdominal Score Responder (secondary efficacy analysis)
4. Linaclotide vs. placebo – Change from Baseline in Abdominal Score at Week 12
5. Linaclotide vs. placebo – Change from Baseline in Abdominal Score at Week 10
6. Linaclotide vs. placebo – Change from Baseline in Abdominal Score at Week 8
7. Linaclotide vs. placebo – Change from Baseline in Abdominal Score at Week 6
8. Linaclotide vs. placebo – Change from Baseline in Abdominal Score at Week 4
9. Linaclotide vs. placebo – Change from Baseline in Abdominal Score at Week 2
10. Linaclotide vs. placebo – Change from Baseline in Abdominal Score at Week 1

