**2.0** **STUDY OBJECTIVES**

The objectives of this study are to evaluate the efficacy on abdominal symptoms (abdominal bloating, abdominal discomfort, and abdominal pain) and safety of linaclotide 290 µg administered orally to patients with irritable bowel syndrome with constipation (IBS-C).

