## **6.6 MULTIPLE COMPARISONS/MULTIPLICITY**

The overall family-wise Type I error rate for the primary and secondary efficacy analyses will be controlled at the  $\alpha=0.05$  level by employing a fixed-sequence procedure as described below. Following the fixed-sequence procedure, if the primary hypothesis between the placebo group and the linaclotide 290  $\mu\text{g}$  group is statistically significant ( $\alpha=0.05$ ) in the ITT Population, then the primary objective of the trial will have been achieved and the next hypothesis can be tested; otherwise, testing will stop. The testing of each sequential hypothesis is conditional on all the previous hypotheses being rejected at the 0.05 level of significance. If a hypothesis is not rejected at the 0.05 level of significance, then all remaining hypotheses are deemed not statistically significant. All hypothesis testing will be two-sided.

1. Linaclotide vs. placebo – Change from Baseline in Abdominal Score
2. Linaclotide vs. placebo – Change from Baseline in 12-week Abdominal Score (CDF)
3. Linaclotide vs. placebo – 6/12 Week Abdominal Score Responder
4. Linaclotide vs. placebo – Change from Baseline in Abdominal Score at Week 12
5. Linaclotide vs. placebo – Change from Baseline in Abdominal Score at Week 10
6. Linaclotide vs. placebo – Change from Baseline in Abdominal Score at Week 8
7. Linaclotide vs. placebo – Change from Baseline in Abdominal Score at Week 6
8. Linaclotide vs. placebo – Change from Baseline in Abdominal Score at Week 4
9. Linaclotide vs. placebo – Change from Baseline in Abdominal Score at Week 2
10. Linaclotide vs. placebo – Change from Baseline in Abdominal Score at Week 1

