## 7.9 EFFICACY ANALYSIS

All efficacy analyses will be based on the ITT Population for the Treatment Period and based on the RW Population for the RW Period.

Baseline values for efficacy parameters will be derived from the eDiary daily data collected in the Pretreatment Period, specifically the period of time from 14 days prior to randomization up to the time of randomization.

A patient's daily abdominal score is calculated as the average of the daily abdominal pain, abdominal bloating, and abdominal discomfort assessments. If two or more of these individual daily abdominal symptoms are missing, then the Abdominal Score for that day will be missing.

Baseline values for patient symptom severity parameters (e.g., abdominal score, abdominal discomfort, abdominal bloating, abdominal pain, and constipation severity) will be the average of the non-missing severity scores reported during this period.

An SBM is defined as a BM that occurs in the absence of laxative, enema, or suppository use on either the calendar day of the BM or the calendar day before the BM. CSBM is defined as an SBM associated with a sense of complete evacuation.

The baseline CSBM and SBM weekly rates will be derived based on the number of CSBMs and SBMs a patient had during this period.

Baseline stool consistency and straining will be calculated as the average of the non-missing values from the SBMs reported by the patient during this period. A patient's baseline Stool Consistency and straining cannot be assessed if the patient does not have at least one SBM during the Pretreatment Period. Patients with missing baseline Stool Consistency will be excluded from Stool Consistency analyses that involve change from baseline. Similarly, patients with missing baseline straining will be excluded from straining analyses that involve change from baseline.

For weekly responder parameters based on daily eDiary assessments, a patient with less than 4 complete evening reports during an analysis week will not be considered a responder for that week.

Trial centers will be pooled by geographic region (details provided in Section 9.3). In lieu of trial center, geographic region will be used in analyses adjusting for center-to-center variability.

All hypotheses will be tested at a two-sided 0.05 significance level (Section 6.6). All confidence intervals will be 2-sided 95% confidence intervals, unless stated otherwise.

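### All ten error-controlled hypotheses test the average of bloating, discomfort and pain, so even full success supports no controlled claim on any one of these named symptoms; three tests appended after hypothesis 10 would close this gap without cost to the existing tests.

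*SAP*

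**What the plan says.** The objective in Protocol section 4 is to "evaluate the efficacy on abdominal symptoms (abdominal bloating, abdominal discomfort, and abdominal pain) and safety of linaclotide 290 µg"; SAP 2.0 says the same. The variable that carries the confirmatory testing is defined in SAP 7.9: the "daily abdominal score is calculated as the average of the daily abdominal pain, abdominal bloating, and abdominal discomfort assessments".

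Protocol 10.4.5 and SAP 6.6 list ten hypotheses in fixed order, each two-sided at 0.05. All are on the Abdominal Score: the overall MMRM comparison, the 12-week change (CDF), the 6/12-week responder, and then Weeks 12, 10, 8, 6, 4, 2 and 1. The last is "Change from Baseline in Abdominal Score at Week 1". The rule is that "The testing of each sequential hypothesis is conditional on all the previous hypotheses being rejected at the 0.05 level of significance". Nothing follows hypothesis 10. Both sections count the primary objective as achieved once hypothesis 1 is rejected.

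Change from baseline in bloating, in discomfort and in pain, and a 6/12-week responder endpoint for each, appear in Protocol 10.4.6 and SAP 7.9.3 as additional endpoints. Of these the SAP states: "Additional efficacy endpoints will be explored outside of the formal testing procedures and not controlled for multiplicity". They are nevertheless analysed with the primary MMRM and the CMH method (Protocol 10.4.7, SAP 7.9.3.1), so estimates, confidence intervals and p-values will be produced.

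**The concern.** A significant average does not say which of its components moved. If the true mean difference on the score favours linaclotide, then at least one of the three symptom differences must do so, but the test does not identify which. The objective lists three symptoms, and the confirmatory family has no step for any of them.

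Equal movement across the three cannot be taken for granted from the entry criteria: Protocol 6.1 sets a minimum average for pain (criterion 9) and none for bloating or discomfort.

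What is at stake is the strength of the conclusion. Three symptom p-values will be available, each at an unadjusted 0.05. Anyone who wants to say that bloating, discomfort or pain improved will have to rely on them. The alpha that remains after hypothesis 10 is passed to nothing.

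**Working it through.** **The plan's own figure.** Protocol 10.8 and SAP 4.0 state more than 99% power for the primary and about 94% for all ten hypotheses, from resampling an earlier Phase 3 trial. The documents give no effect size, SD or correlation from that trial, so these figures cannot be reproduced. They are taken as stated below.

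**Inputs.** 300 per group, 1:1, two-sided 0.05 (Protocol 10.8, 7.3 and 10.4.5). The only single-symptom effect in the documents is the Phase 2b pain result in Protocol 3.3: −1.9 against −1.4, a difference of 0.5 points. No SD is given. Assumption: SD of change 2.0, range 1.5 to 2.5.

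**1. Error rate of the symptom tests as planned.** With three unadjusted tests and no symptom effect, the chance of at least one false finding is 1 − 0.95³ = 14.3% if the tests are independent. By simulation it is about 9.8% at an assumed correlation of 0.8.

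**2. Error rate with the three tests appended.** If any of hypotheses 1 to 10 is a true null, a false rejection anywhere requires the first such null to be rejected, which has probability at most 0.05. If all ten are truly non-null, the only possible false rejections are among the three symptoms, and a fixed order or Holm at 0.05 limits these to 0.05. Family-wise error therefore stays at or below 0.05. Simulation with one million runs agrees:

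- Global null: 0.0498.
- First ten effects overwhelming, all three symptoms null: 0.0497 in fixed order, 0.035 to 0.049 with Holm.

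**3. Effect on hypotheses 1 to 10.** None. Each is tested before the added steps, at the same level and under the same conditions, so the stated 94% is unchanged.

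**4. Power of one symptom test alone.** SE = SD × √(2/300); power = Φ(0.5/SE − 1.96).

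| SD | SE | 0.5/SE | Power |
|---|---|---|---|
| 1.5 | 0.122 | 4.08 | 98% |
| 2.0 | 0.163 | 3.06 | 86% |
| 2.5 | 0.204 | 2.45 | 69% |

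**5. Power once the first ten steps are counted.** Whatever the correlation, the chance that all ten succeed and the first symptom test also rejects lies between 0.94 + power − 1 and the smaller of 0.94 and power:

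- SD 1.5: 92% to 94%.
- SD 2.0: 80% to 86%.
- SD 2.5: 63% to 69%.

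This combines the plan's 94%, from one trial, with a 0.5-point effect from another, so it is only a guide.

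**6. Power for all three symptoms.** This was simulated with equal expected z for the ten score tests, scaled so that all ten reject in 94% of trials, and correlations of 0.6 to 0.9 (all assumed). The symptom tests are in fixed order.

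| Symptom z as share of score z | First symptom | All three |
|---|---|---|
| 100% | about 94% | 93% to 94% |
| 80% | 88% to 90% | about 83% |
| 70% | 79% to 83% | 70% to 71% |

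**The case against.** The best defence is that the plan is coherent as it stands. The objective is efficacy on abdominal symptoms, with the three listed in parentheses; it does not promise a claim on each. The primary endpoint averages exactly those three. The single-symptom endpoints are openly labelled as uncontrolled, so nobody is misled. All of that stands, and it is why this is a limit on claims and not an error.

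A reader might go further and infer three things that the documents do not support.

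- **That a symptom with no effect could be hidden behind the other two.** Each symptom has its own pre-specified estimate and confidence interval, so a null component would be visible. At the assumed SD of 2.0, the score would be significant at an observed difference of 1.96 × 0.163 = 0.32 points, which two symptoms at 0.48 and one at zero would produce. But that is only the threshold of hypothesis 1, not of all ten. It also sits badly with the stated power: in a simple two-group model, more than 99% needs a difference of at least (1.96 + 2.33) × √(2/300) = 0.35 SD, or 0.70 points at SD 2.0. Two symptoms would then have to average 1.05 with the third at zero.
- **That the trial weakens the evidence on each symptom.** Protocol 3.3 reports improvement in bloating, discomfort and pain in both registration trials, at p<0.01 with multiplicity control. That evidence remains, and it makes it defensible for a Phase 3b trial to spend its family on the composite and its time course.
- **That the seven single-week tests crowd out the symptoms.** They do not; steps can be added at the end without removing any.

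One objection bears on the remedy. Control would exist only if all ten score tests succeed, including Week 1. In a fixed order an early symptom failure also blocks the later ones, so the order needs a reason, or Holm should be used.

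**Conclusion.** The point holds as a limit on what the trial can conclude. With all ten hypotheses rejected, the controlled conclusion is that abdominal symptoms improved jointly, meaning at least one of the three, but no single symptom can be named. Nothing else in either document supplies that control.

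The gap can be closed at no cost to the existing tests. That part rests on the structure of the sequence and needs no assumption about effects. How often the added tests would succeed does depend on assumptions. They are reached about 94% of the time on the plan's own figure. Each alone has about 86% power at 0.5 points and SD 2.0, and 98% to 69% over SDs of 1.5 to 2.5. The 0.5 is a pain result, and applying it to bloating and discomfort is an assumption, as are the SDs and correlations.

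This is a worthwhile free improvement. It does not call the choice of primary endpoint into question.

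**What to change.** Before unblinding:

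1. In SAP 6.6 and Protocol 10.4.5 (and the matching Synopsis text), append after hypothesis 10 the Treatment Period MMRM comparisons of change from baseline in abdominal bloating, abdominal discomfort and abdominal pain. Test them in an order that the sponsor pre-specifies and justifies, or by Holm across the three.
2. Amend SAP 7.9.3 and Protocol 10.4.6 so that these three analyses are no longer listed as uncontrolled. The by-week and responder analyses of the single symptoms can stay as they are.
3. State that a claim on a single symptom requires rejection of its own hypothesis.

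The cost is a few lines of text and a protocol amendment. The data and models are already planned, and the tests must go at the end: placed earlier, they would lower the power of the tests behind them. If the sponsor prefers not to add them, the SAP should say that single-symptom results are descriptive and support no individual symptom claim.
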